## Sample size

*Describe the sample size of your study. How many units will be analyzed in the study? This could be the number of people, birds, classrooms, plots, interactions, or countries included. If the units are not individuals, then describe the size requirements for each unit. If you are using a clustered or multilevel design, how many units are you collecting at each level of the analysis?*

The final analyzed sample size is expected to be BPT = 27, CET = 27. BPT collection is complete; the last CET group is anticipated to be complete in May/June 2017.

## Sample size rationale

*This could include a power analysis or an arbitrary constraint such as time, money, or personnel.*

Families recruited between June 2013 and December 2014 were offered behavioral parent training (BPT). The final BPT post-treatment session was completed in June 2015. Families recruited between June 2015 and December 2016 were offered central executive training (CET). The final CET post-treatment session was completed in [TBD, likely May/June] 2017. Recruitment to CET was closed when the software for the active comparator was completed. We are currently conducting a pilot randomized trial of CET versus this active comparator (inhibition training).

## Stopping rule

*If your data collection procedures do not give you full control over your exact sample size, specify how you will decide when to terminate your data collection.*

Recruitment to BPT was stopped when CET was ready for testing. Recruitment to CET was stopped when the active comparator was ready for testing. Families are now being recruited to a pilot RCT of CET vs. this active comparator. That trial is registered at clinicaltrials.gov (NCT03042338).

## Variables

### Manipulated variables

*Describe all variables you plan to manipulate and the levels or treatment arms of each variable. For observational studies and meta-analyses, simply state that this is not applicable.*

#### Treatments

##### Behavioral Parent Training (BPT)

Evidence-based behavioral parent training (BPT; Evans et al., 2014) was provided using the Barkley (2013) Defiant Child protocol. BPT was delivered with fidelity in small group format by behaviorally trained, PhD-level clinicians ([name], [name], [name]).

##### Central Executive Training (CET)

CET is a translational, evidence-informed, hybrid (in-office and at-home), software-based treatment protocol that includes gaming elements and an automated token economy to reinforce training goals and improve player engagement. The final 10-week protocol includes weekly, in-office sessions with the child (1 hour) and a concurrent parent psychoeducational group, combined with parent-supervised, in-home training (goal: 15-min/day, 2-3 days/week).

CET beta testing. The CET sample was recruited in 3 waves to facilitate software refinements and testing of key design features. As specified in the NIH grant proposal (R34 MH102499), the first subgroup trained on one game per week, the second subgroup had immediate access to all 9 training games, and the third subgroup (approximate n=9 per subgroup) received the final protocol that implemented all CET features. To reduce child expectancies, children were told that they were "beta testers" for our video game design team. Breadth of training across the 9 games was facilitated by a software algorithm that limited initial access each day to three games the child had not completed recently (third

subgroup only). Children earned additional rewards and access to all nine games for completing this daily "Mission Mode." Leveling was set to ensure incremental increases in difficulty based on child performance. This process occurred during the current study and involved iterative changes and extensive testing with graduate/undergraduate Research Assistants (alpha testing) and children with ADHD (beta testing).

CET focus groups. Caregivers in the first two CET subgroups participated in focus groups. Key CET design changes based on these focus groups included overhauling the on-screen instructions, modifying the home screen to show child progress (daily games completed), and automation of the token economy via children earning on-screen 'tickets' that are exchanged for tangible, in-office rewards. Key logistical changes from these focus groups included improved communication with caregivers (e.g., access/login instructions, progress monitoring of days/games completed at home), modified expectations for at-home training duration (original goal of 30-minutes/day decreased to 15-minutes/day) and frequency (original daily training goal decreased to 2-3 days/week), and modified treatment duration (original 12-weeks decreased to 10-weeks). Finally, caregiver feedback resulted in the addition of a caregiver psychoeducational group that began mid-way through testing with subgroup 2. Most caregivers described homework as the biggest obstacle to at-home CET training; opinions were split approximately evenly regarding priority of CET vs. homework, with differences focused primarily on weighing immediate vs. delayed consequences.

no file selected

## Measured variables

*Describe each variable that you will measure. This will include outcome measures, as well as any predictors or covariates that you will measure. You do not need to include any variables that you plan on collecting if they are not going to be included in the confirmatory analyses of this study.*

### Measures

#### Intellectual Functioning (IQ)

IQ was estimated using the Verbal Comprehension Index from the WASI-II (BPT) or WISC-V (CET) (Wechsler, 2011, 2014). The changeover was made to provide caregivers the most up-to-date evaluation possible. Standard scores are used.

#### Socioeconomic Status (SES)

Hollingshead (1975) SES was estimated based on caregiver(s)' education and occupation.

#### Primary Outcomes (Working Memory)

The Rapport et al. (2009) computerized working memory tests correctly classify children with vs. without ADHD at similar rates as parent and teacher ADHD rating scales (Tarle et al., 2017), and predict hyperactivity (Rapport et al., 2009), inattention ([name] et al., 2010), and impulsivity (Raiker et al., 2012). Reliability and validity evidence includes internal consistency ( $\alpha=.82-.97$ ), 1-3-week test-retest reliability (.76-.90; Sarver et al., 2015), and expected relations with criterion working memory complex span ( $r=.69$ ) and updating tasks ( $r=.61$ )(Wells et al., under review). Six trials per set size were administered in randomized/unpredictable order (3-6 stimuli/trial; 1 stimuli/second) as recommended ([name] et al., 2016). Five practice trials were administered before each task (80% correct required). Task duration was approximately 5 (visuospatial) to 7 (phonological) minutes.

Phonological working memory. Children were presented a series of jumbled numbers and a letter (1 stimuli/second). The letter was never presented first or last to minimize primacy/recency effects, and was counterbalanced to appear equally in the other serial positions. Children reordered and recalled the numbers from least to greatest, and said the letter last (e.g., 4H62 is correctly recalled as 246H). Two trained research assistants, shielded from child view, independently recorded oral responses. Interrater reliability will be computed (% agreement = % of trials for which both RAs transcribed the identical sequence).

Visuospatial working memory. Children were shown nine squares arranged in three offset vertical columns. A series of 2.5 cm dots were presented sequentially (1 stimuli/second); no two dots appeared in the same square on a given trial. All dots were black except one red dot that never appeared first or last to minimize primacy/recency effects. Children reordered the dot locations (black dots in serial order, red dot last) and responded on a modified keyboard.

Dependent variables. Stimuli correct per trial were computed at each set size as recommended (Conway et al., 2005), and averaged to provide a single indicator for each task. Higher scores reflect better working memory.

#### Secondary Outcomes (ADHD Symptoms)

Subjective report. Parent-reported Attention Problems and Hyperactivity/Impulsivity T-scores on the BASC-2 (age and gender norms) served as the primary subjective assessment of treatment effects on ADHD symptoms.

Objective measurement. Basic Motionlogger® (Ambulatory Monitoring, 201x) are acceleration-sensitive devices that sample movement intensity 16 times per second (16 Hz), collapsed into 1-second epochs. The estimated reliability for

actigraphs placed at the same site on the same person ranges from .90 to .99 (Tryon et al., 1991). Children were told that the actigraphs were "special watches" that let them play the computer learning games. Observer XT (Noldus, 201X) software was used to code start and stop times for each task, which were matched to the time stamps from the actigraphs.

Actigraphs were placed on the child's non-dominant wrist and both ankles using Velcro watch bands. Following Rapport et al. (2009), a total hyperactivity score was computed by summing activity level across the three actigraphs. Hyperactivity scores were computed separately for movement during each of the working memory tests described above, as well as for movement during the control conditions that occurred as the first and last activities of each testing session. Movement scores reflect movement intensity (Proportional Integrating Measure; PIM).

During these control conditions, children used Microsoft Paint for five consecutive minutes at the beginning and end of all pre- and post-treatment sessions. Children sat in the same chair and interacted with the same computer used for the working memory tasks while interacting with a program that placed relatively modest demands on working memory (i.e., the Paint program allows children to draw/paint anything they like on the monitor using a variety of interactive tools).

#### Feasibility/Acceptability Outcomes

Client Satisfaction Questionnaire (CSQ-8; Nguyen et al., 1983). The CSQ-8 is an extensively studied, 8-item generic measure of clients' perceptions of the value of services received. Parents completed the CSQ-8 at post-treatment. Total scores will be used.

Barriers to Treatment Participation Scale (BTPS; Kazdin et al., 1997). The BTPS is a 44-item measure of perceived treatment barriers; item scores are summed to provide a Total Barriers score and 4 subscores: (1) Stressors/obstacles; (2) Treatment demands/issues; (3) Perceived relevance; and (4) Relationship with the Therapist. Parents completed the BTPS at post-treatment. Total scores will be used for each subscale.

System Usability Scale (SUS; Canon-Bowers & Bowers, 2010). The SUS is a 10-item, IRT-developed scale assessing ease of use on a 5-point Likert scale. Children in the CET group completed the SUS each week for a different training game, and at post-treatment for the CET system overall. Total scores will be used.

CET Training Duration. The CET software records training duration for each completed training task; total minutes trained and total completed games are reported.

no file selected

## Indices

*If any measurements are going to be combined into an index (or even a mean), what measures will you use and how will they be combined? Include either a formula or a precise description of your method. If your are using a more complicated statistical method to combine measures (e.g. a factor analysis), you can note that here but describe the exact method in the analysis plan section.*

Described for each measure above.

no file selected

## Design Plan

### Study type

*Please check one of the following statements*

Experiment - A researcher randomly assigns treatments to study subjects, this includes field or lab experiments. This is also known as an intervention experiment and includes randomized controlled trials.

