#### Study Timeline

Children were not randomized to treatment condition. Families recruited between June 2013 and December 2014 were offered behavioral parent training (BPT). The final BPT post-treatment session was completed in June 2015. Families recruited between June 2015 and December 2016 were offered central executive training (CET). The final CET post-treatment session was completed in [TBD, likely May/June] 2017. Recruitment to CET was closed when the software for the active comparator was completed. We are currently conducting a pilot randomized trial of CET versus this active comparator (inhibition training).

Identical procedures were used for both samples. Both treatments were delivered in small group format (2-4 families) or individually as needed to accommodate families' schedules. Schedule changes were accommodated to the extent possible (e.g., make-up sessions the same week).

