## Study design

*Describe your study design. Examples include two-group, factorial, randomized block, and repeated measures. Is it a between (unpaired), within-subject (paired), or mixed design? Describe any counterbalancing required. Typical study designs for observation studies include cohort, cross sectional, and case-control studies.*

Sequential, non-randomized design. The BPT sample was recruited while PI [name] was at the University of Virginia. Data collection continued, led by co-PI [name], when PI [name] changed institutions to Florida State University in August, 2014. The CET sample was collected at FSU (co-PI [name] for 2015-2016, co-PI [name] for 2016-present). Identical procedures were used for both samples. Both treatments were delivered in small group format (2-4 families) or individually as needed to accommodate families' schedules. Schedule changes were accommodated to the extent possible (e.g., make-up sessions the same week). Families recruited between June 2013 and December 2014 were offered behavioral parent training (BPT). The final BPT post-treatment session was completed in June 2015. Families recruited between June 2015 and December 2016 were offered central executive training (CET). The final CET post-treatment session was completed in [TBD, likely May/June] 2017. Recruitment to CET was closed when the software for the active comparator was completed. We are currently conducting a pilot randomized trial of CET versus this active comparator (inhibition training) that is registered at clinicaltrials.gov (NCT03042338).

no file selected

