## Randomization

*If you are doing a randomized study, how will you randomize, and at what level?*

Participants are not randomized because the CET intervention was in development. Recruitment to BPT was closed when CET was ready for testing. Recruitment to CET was closed when the active comparator was ready for testing.

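### A non-significant baseline-adjusted comparison is read as equivalence with no margin, and the inference text sets no limit for two non-randomised, sequential cohorts

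*Combined protocol and SAP*

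**What the plan says.** **Equivalence and non-inferiority.** Recommended elements appears twice, once after the hypotheses (item 1) and once in the Analysis Plan (item 10). Both versions turn to the post-treatment score adjusted for the pre-treatment score and end by saying that finding no differences there means the interventions are equivalent. Neither gives a margin. Inference criteria sets p at .05 and a Bayes factor of 3 as thresholds, reports whichever of BF10 and BF01 exceeds 1, and lets the p-value prevail when the two disagree. Research question 3 asks whether the improvement in ADHD symptoms with CET is non-inferior to that with BPT. The matching analysis (Analysis Plan, Secondary Outcomes, item 2) is a group x time ANOVA with its post-hoc tests.

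**Design.** Study design says "Sequential, non-randomized design". Study Timeline says "Children were not randomized to treatment condition". Randomization says "Participants are not randomized because the CET intervention was in development". BPT families were recruited from June 2013 to December 2014 and CET families from June 2015 to December 2016. Covariates and Data Handling (item 1) adjusts for pre-treatment characteristics that differ significantly between arms after correction.

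**Study type.** The option shown in this field is an experiment in which "A researcher randomly assigns treatments to study subjects, this includes field or lab experiments".

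**The concern.** A non-significant test shows that the data did not exclude zero. It does not show that the difference is small. Without a margin, nothing in the plan says how large a difference is still compatible with calling two treatments equivalent. A wide confidence interval therefore makes an equivalence reading easier to reach. The sentence is also the plan's only stated rule for interpreting a null comparison between arms, so in practice it would be used to answer the non-inferiority question too.

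The second issue is what any between-arm result can mean. A group x time effect here is a difference between two cohorts recruited at different times. It is a treatment effect only if period, and site where site follows arm, did not influence change. The text on inference does not say so. Unqualified statements of superiority, non-inferiority or equivalence could therefore all be made within the plan.

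**Working it through.** **The plan's own figures.** There is no power, effect size, SD or margin to reproduce. The sample size was set by when the software became ready (Sample size rationale, Stopping rule).

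**Inputs**
- n = 27 per arm, expected (Sample size).
- Significance level .05 (Inference criteria). Sidedness is not stated, so two-sided is assumed.
- Pre-post correlation r = .5, .7, .76 and .90, all assumed. The last two are the ends of the 1-3-week test-retest range given under Primary Outcomes (Working Memory). That range covers the working memory tests only, and treatment lasts longer (10 weeks in the final CET protocol), so the true r may be lower.
- True differences of 0.3 and 0.5 SD of the raw post-treatment score, assumed.

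**Formulas**, for ANCOVA with the pre-treatment score as the only covariate and balanced baselines:
- Residual SD = sqrt(1 - r²), in raw SD units.
- df = 54 - 3 = 51; critical t = 2.008.
- 95% half-width = 2.008 x sqrt(2/27) x sqrt(1 - r²) = 0.546 x sqrt(1 - r²).
- Noncentrality = difference x sqrt(27/2) / sqrt(1 - r²) = 3.674 x difference / sqrt(1 - r²). The chance of a non-significant result follows from the noncentral t distribution.

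Example: r = .7 and difference 0.5 give 3.674 x 0.5 / 0.714 = 2.57, and the test is non-significant in 29% of studies.

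| r | sqrt(1 - r²) | 95% half-width (SD) | Missed, true 0.3 SD | Missed, true 0.5 SD |
|---|---|---|---|---|
| .5 | 0.866 | 0.47 | 76% | 45% |
| .7 | 0.714 | 0.39 | 67% | 29% |
| .76 | 0.650 | 0.36 | 62% | 21% |
| .90 | 0.436 | 0.24 | 30% | 1.5% |

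An observed difference of exactly zero would thus still be compatible with true differences of about 0.24 to 0.47 SD in either direction.

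**Period and site.** The two recruitment windows do not overlap; January to May 2015 lies between them. Knowing a family's period is the same as knowing its arm, so no model can estimate both effects. The candidate covariates are child and family characteristics measured before treatment, and none of them breaks that link. On site, Study design says that the PI "changed institutions to Florida State University in August, 2014" and that "The CET sample was collected at FSU". It places BPT recruitment in the PI's time at the first university but also says that data collection continued under a co-PI after the move. BPT recruitment ran to December 2014, and the site of the later BPT families is not named. Site therefore probably follows arm, but this is not settled.

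**Study type.** Three sections (Study Timeline, Study design, Randomization) say there was no randomisation; one form field says there was. The field is the one that is wrong.

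**The case against.** The strongest reply concerns size. For the primary outcome the plan's own reliability range points to high pre-post correlation, and at r = .90 the adjusted test rarely misses 0.5 SD. That stands. A reader who runs an unadjusted change-score t-test at 27 per arm would obtain 56% non-significance at 0.5 SD, and might quote that. It should not be used here: it is in SDs of change and belongs to a different test from the baseline-adjusted one that the equivalence sentence names. But even at r = .90 a true 0.3 SD difference is missed in 30% of studies. The reliability range also does not cover the parent ratings on which research question 3 rests.

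BF01 could provide evidence for a null. The equivalence sentence does not require it, however, and the p-value prevails when they disagree.

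Inference criteria asks for thresholds, not causal caveats, and the design facts are disclosed elsewhere. That is fair as to disclosure, but disclosing the design does not limit the conclusion. The opposite predictions (CET better on working memory, BPT better on oppositional symptoms) also help, since a general cohort shift would not readily produce both. They lessen the confounding worry without removing it.

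Two stronger readings are tempting. One is that the registration presents the study as a randomised trial or conceals its design. The three explicit statements of non-randomisation rule that out, and no analysis depends on the Study type field. The other is that "Identical procedures were used for both samples" is contradicted by undisclosed differences. The known exceptions, the mid-treatment session and the IQ instrument, are stated under Procedures and Intellectual Functioning (IQ).

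**Conclusion.** The equivalence sentence is wrong as written, and the non-inferiority question cannot be answered by the planned analysis. This conclusion is logical and does not depend on the figures. The figures show how much it could matter: at a true 0.5 SD difference the chance of a false equivalence reading runs from about 45% down to 1.5%, and at 0.3 SD from about 76% to 30%, as the assumed pre-post correlation rises from .5 to .90. They assume 27 per arm, a two-sided test, one covariate and balanced baselines.

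The missing limit on causal reading is a real gap, because arm and period coincide completely. How much period or site affected change cannot be estimated from the documents, so no size is attached. The Study type entry is a minor form error. That site is wholly confounded with arm is something a reader might infer, but the documents support only that this is probable.

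**What to change.** 1. Delete the equivalence sentence from both Recommended elements lists. State in the Analysis Plan version and in Inference criteria: *A non-significant difference will be reported as no difference detected, with its 95% confidence interval, and not as equivalence or non-inferiority.*
2. For research question 3, either set and justify a margin before the data are analysed and judge it by the confidence interval, or reword the question as an estimated difference. The co-PIs without data access could set it. A margin may not be achievable at this size. With an assumed margin of 0.5 SD (illustration only), one-sided .025, 80% power and no true difference, the need is 2 x (1.96 + 0.842)² / 0.25 = 63 per arm unadjusted, or about 33 after multiplying by 1 - 0.7² = 0.51 for an assumed r of .7.
3. Add to the same two places: *Group x time results are differences between two non-randomised, sequential cohorts with non-overlapping recruitment periods. The baseline covariates cannot separate treatment from period. Causal statements are conditional on period, and site where it follows arm, not having affected change.*
4. Change the Study type entry to a non-randomised type, or annotate it if the form has no such option.

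The cost is wording and, if chosen, justification of a margin. No new data are needed. The downside is a more modest headline claim.
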